Delayed Surveillance Colonoscopy following Piecemeal EMR – a Randomized Study

Study approval Number- RMB-0069-25

Document Date- 17/12/2025

Abstract

Background

Colorectal cancer (CRC) is a major cause of cancer-related morbidity and mortality. Piecemeal endoscopic mucosal resection (pEMR) is an effective treatment for large non-pedunculated colorectal polyps (LNPCPs), which are high-risk precursors of CRC. Previous data have shown that residual and recurrent adenoma (RRA) may occur in 15–30% of cases following pEMR. Accordingly, current guidelines recommend intensive follow-up, which can cause patient morbidity and lack of compliance and financial healthcare burdens. Recent advances in EMR techniques, particularly margin ablation, have significantly reduced RRA rates to approximately 5%. In a recent retrospective analysis, we found that delayed surveillance (12 months post-EMR) was not associated with higher recurrence rates compared to early surveillance (3–6 months). This prospective randomized trial aims to confirm and validate these findings.

Objectives and Hypotheses

To evaluate whether a relaxed surveillance strategy involving fewer colonoscopies (12 and 48 months) is non-inferior to the standard intensive strategy (6, 18, and 48 months) in management of residual or recurrent disease.

Hypothesis: A relaxed surveillance protocol does not increase the rate of residual or recurrent adenoma detected at long-term follow-up, in patients undergoing pEMR of LNPCPs with margin ablation.

Methods

This multicenter prospective randomized controlled trial will enroll approximately 760 patients undergoing pEMR for LNPCPs at Rambam Health Care Campus, Tel Aviv Sourasky Medical Center (Ichilov Hospital), Nazareth Holy Family Hospital and HaEmek Medical Center (Afula). Detailed clinical, endoscopic, and histologic data will be collected on lesion morphology, size, histopathology, and procedural techniques.

Patients will be randomized into two surveillance groups: **the Standard Surveillance Group**: Colonoscopies at 6, 18, and 48 months after the index procedure and **the Relaxed Surveillance Group**: Colonoscopies at 12 and 48 months after the index procedure (similar to surveillance protocols following en-bloc excision by ESD)

Significance and Relevance to Cancer Care

This study directly addresses a major clinical question in post-polypectomy surveillance: whether all patients require early intensive follow-up after piecemeal EMR. If the relaxed surveillance approach proves non-inferior, it may support a revision of current guidelines. This would result in fewer colonoscopies, reduced burden on patients and health systems, improved adherence, and lower costs—without compromising oncologic safety. The findings of this trial may contribute to the development of more efficient and personalized follow-up strategies in colorectal cancer prevention, with the potential to influence future clinical practice guidelines and national health policy.

Background and Aim

Colorectal cancer (CRC) is among the most common cancers globally, with significant morbidity and mortality [1]. Numerous studies have demonstrated that removing colorectal polyps reduces the incidence and mortality of CRC [2]. Large non-pedunculated colorectal polyps (LNPCPs) are considered high-risk precursors of colorectal cancer. Piecemeal endoscopic mucosal resection (pEMR) is the recommended treatment for most non-invasive LNPCPs according to societal guidelines, due to its excellent safety and efficacy profile [3,4,5,6].

One major drawback of colonic pEMR is the potential for residual and recurrent adenoma (RRA). Studies have shown that RRA occurs in 15-30% of cases, with risk factors including high-grade dysplasia, lesion size, lesion location, intra-procedural bleeding, and previous attempts at removal [7,8,9]. Recurrence at the first surveillance colonoscopy (SC1) can be identified endoscopically with high accuracy [10], and endoscopic treatment during SC1, which includes re-excision of the RRA with or without ablation, results in a very low residual RRA rate (2%-4%) at the second surveillance colonoscopy (SC2) [7].

Recent data suggests that RRA can be significantly reduced by systematically applying ablative measures to the post-EMR resection margin. Multiple studies show that in expert hands, the risk of RRA at SC1 can be reduced to 3-5% [6,7,8,12,13]. Currently, an intensive follow-up schedule is recommended following pEMR, with SC1 performed 3-6 months after the initial procedure and SC2 one year after SC1. However, this intensive follow-up places additional burdens on both patients and the healthcare system and may hinder patient compliance [9]. Given that with the advent of margin ablation, RRA rates at SC1 are extremely low, the impact of early surveillance on long-term recurrence rates may be minimal.

We recently completed a retrospective study to evaluate this hypothesis. The study showed no significant difference in recurrence rates between the standard group, which underwent surveillance after 3-6 months, and a group of patients who had delayed surveillance (mean follow-up of 11 months).

The aim of this study is to confirm and validate these findings, in a prospective randomized study. This will solidify the results we observed in our previous retrospective study and potentially lead to a less intensive surveillance strategy.

Methods

Study Design:

We will conduct a multicenter, prospective, non-inferiority randomized study in four academic centers in Israel: Rambam Health Care Campus, Tel Aviv Sourasky Medical Center (Ichilov Hospital), Nazareth Holy Family Hospital and HaEmek Medical Center. Following complete pEMR of a LNPCP, participants will be randomly assigned to either the standard surveillance protocol or the relaxed surveillance protocol. Patients will be consented prior to the EMR procedure.

Randomization – computer-generated dynamic block randomization with a 1:1 allocation ratio will be performed to achieve balance of multiple baseline covariates including: demographic data, procedural data, and lesion characteristics.

Patients:

We will include adult patients who undergo pEMR for LNPCPs (≥ 20 mm) and provide informed consent. Inclusion criteria include

- Adults aged 18 years and older.
- Undergoing pEMR of LNPCPs.
- Able to provide informed consent and comply with follow-up requirements.

Exclusion criteria include:

- Patients with invasive cancer identified during the index procedure.
- en bloc resection.
- Patients unable to attend follow-up colonoscopies due to comorbid conditions.

- Patients who require additional surgery for polyp removal or other complications.

Informed Consent:

Before enrollment, each patient will receive a detailed explanation about the study. They will be given the opportunity to ask questions and discuss any concerns. Written informed consent will be obtained from all participants prior to any study-related procedures.

Procedures:

All pEMR procedures and surveillance colonoscopies will be performed by experienced endoscopists trained in pEMR techniques. Specifically, [name] was lead author on the randomized trial on margin ablation [13] and practiced this technique routinely since early 2016. Procedures will be conducted using high-definition endoscopes (Olympus 190 series Q190 PCF/CF or Fuji 760 series), following a standardized protocol:

1. Inspection and photo documentation of LNPCPs with high-definition white light (HDWL) and optical chromoendoscopy before resection to exclude features suggestive of deep submucosal invasion.
2. Standard pEMR technique with the objective of complete snare excision, using sub-mucosal injections of Succinylated Gelatine (Gelofusin) or Normal Saline and braided snares of various sizes.
3. Thermal ablation of the mucosal defect margin using snare soft tip coagulation (STSC) to create a 2- to 3-mm rim of ablated tissue.

Groups and Follow-Up:

- Standard Surveillance Group: Patients will undergo surveillance colonoscopy at 6 and 18 months after the index procedure. The standard surveillance group will have an additional colonoscopy at 48 months in order to converge the timeline with the delayed group.
- Relaxed Surveillance Group: Patients will undergo surveillance colonoscopy at 12 and 48 months after the index procedure.

Data Collection:

We will collect demographic data, lesion characteristics, procedural details, and surveillance outcomes. All recurrences will be identified using endoscopic evaluation. Routine biopsies will be taken only when recurrence is suspected endoscopically, based on a validated approach that has shown a negative predictive value (NPV) of 99% for identifying normal scars without recurrence [14].

Data Management, Storage and Security:

All data will be collected on data collection forms. These will be stored in a locked cabinet at the Gastroenterology department. This data will be entered into electronic data sheets (Excel and Redcap). The electronic files will be password protected and stored on a password-protected computer in the Gastroenterology department. Access to the data will be given to the study investigators and the study research assistant.

Primary Endpoint

The primary endpoint is the rate of residual or recurrent adenoma at the second surveillance colonoscopy (SC2), comparing the relaxed and standard surveillance groups.

Secondary Endpoints

Secondary endpoints include: recurrence rates at SC1; risk factors associated with recurrence; subgroup analysis of high risk lesions (e.g., high-grade dysplasia, sessile serrated morphology); rates of new or missed polyps at SC2; adverse events related to EMR or surveillance procedures; and comparative cost effectiveness of both surveillance strategies.

Timetable

We anticipate 4-5 years are required to complete the study: 1-2 years for recruitment and an additional 36 months for follow-up to SC2.

Funding and Competing Interests

There are no disclosures. No commercial funding is sought. We will apply for research grants to help with study funding, specifically research assistant salary and management of the electronic database.

References:

1. Siegel, R. L. et al. Colorectal cancer statistics, 2020. *CA. Cancer J. Clin.* 70, 145–164 (2020).
2. Zauber, A. G. et al. Colonoscopic polypectomy and long-term prevention of colorectal-cancer deaths. *N. Engl. J. Med.* 366, 687–96 (2012).
3. Ferlitsch, M. et al. Colorectal polypectomy and endoscopic mucosal resection (EMR): European Society of Gastrointestinal Endoscopy (ESGE) Clinical Guideline. *Endoscopy* 49, 270–297 (2017).
4. Jayanna, M. et al. Cost Analysis of Endoscopic Mucosal Resection vs Surgery for Large Laterally Spreading Colorectal Lesions. *Clin. Gastroenterol. Hepatol.* 14, 271-8 (2016).
5. Bahin, F. F. et al. Wide-field endoscopic mucosal resection versus endoscopic submucosal dissection for laterally spreading colorectal lesions: a cost-effectiveness analysis. *Gut* 67, 1965–1973 (2018).

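### The primary endpoint is set at SC2, which by the protocol's own schedules is month 18 in the standard arm and month 48 in the relaxed arm

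*Protocol*

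**What the plan says.** The objective is to learn whether the relaxed strategy "is non-inferior to the standard intensive strategy (6, 18, and 48 months) in management of residual or recurrent disease". The hypothesis beneath it reads "A relaxed surveillance protocol does not increase the rate of residual or recurrent adenoma detected at long-term follow-up", so the question is a long-term one. Study Design confirms the type of trial: "We will conduct a multicenter, prospective, non-inferiority randomized study".

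The schedules stand in the abstract's Methods and again in Groups and Follow-Up. The standard arm is examined at 6 and 18 months. It then has an extra colonoscopy at 48 months, and the reason given is to bring its timeline into line with the other arm. The relaxed arm is examined at 12 and 48 months.

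The Primary Endpoint section compares the arms on the rate of residual or recurrent adenoma at SC2, which it defines as the second surveillance colonoscopy. It names no month. Background and Aim uses the same label for the current intensive schedule: "SC1 performed 3-6 months after the initial procedure and SC2 one year after SC1". The Timetable allows 1-2 years for recruitment plus 36 months of follow-up to SC2, 4-5 years in all.

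**The concern.** SC2 is a visit number, and the arms reach their second visit at different times. A comparison by visit number therefore sets an early examination in one arm against a late one in the other. A difference between arms, or the lack of one, could then come from when the examination took place and not from the surveillance strategy.

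This matters because the primary result is meant to carry weight in practice: "If the relaxed surveillance approach proves non-inferior, it may support a revision of current guidelines". A verdict at unequal times does not answer the long-term question in the hypothesis. It also leaves unused, for the primary comparison, the 48-month standard-arm visit that was added to make the arms comparable. The secondary endpoint on new or missed polyps is also set at SC2 and has the same problem.

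**Working it through.** **Inputs, all from the protocol.** Standard arm: months 6, 18 and 48. Relaxed arm: months 12 and 48. Recruitment: 1-2 years. Follow-up to SC2: 36 months. Stated duration: 4-5 years.

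**Step 1: locate SC2.** The second examination is month 18 in the standard arm and month 48 in the relaxed arm. The Background supports this for the standard arm: SC2 comes one year after SC1, and 6 + 12 = 18.

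**Step 2: time since the previous colonoscopy** (month of the examination minus month of the one before).

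| Comparison | Standard | Relaxed |
|---|---|---|
| At SC2 as written | 18 - 6 = 12 months | 48 - 12 = 36 months |
| At the common 48-month visit | 48 - 18 = 30 months | 48 - 12 = 36 months |

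At SC2 the gap is three times as long in the relaxed arm (36/12 = 3). At month 48 it is 1.2 times as long (36/30 = 1.2), and that remaining difference belongs to the strategies being compared.

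**Step 3: what drops out.** With SC2 at month 18, the standard arm's last 48 - 18 = 30 months do not enter the primary comparison.

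**Step 4: direction of bias.** If recurrence keeps appearing with time, the later look counts against the relaxed arm. If the standard arm's 18-month examination finds recurrence that is treated and stays cleared, its 18-month rate overstates its 48-month rate, and the comparison favours the relaxed arm. The protocol gives no rates by month that would settle which applies.

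**Step 5: the timetable.** The stated figure reproduces: 1-2 years + 36 months (3 years) = 4-5 years. But 36 months is neither arm's SC2 counted from the index procedure (18 or 48). It equals only the relaxed arm's interval from its first to its second examination, 48 - 12 = 36. The last patient recruited to the relaxed arm still needs 48 months, so the duration is 1-2 years + 4 years = 5-6 years.

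**Step 6: the statements side by side.** The endpoint, read literally, gives 18 versus 48 months. The hypothesis speaks of long-term follow-up, the extra standard-arm visit exists to align the arms at 48 months, and the timetable implies 36 months. These cannot all describe one primary comparison.

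**The case against.** The strongest reply is that month 48 in both arms was intended all along. The extra standard-arm visit and the long-term hypothesis both point that way, and SC2 may be only a slip of labelling. This is plausible, but it does not cure the text: the endpoint names SC2, and the Background uses that label for a visit one year after SC1.

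A second reply is that at SC2 each arm has had exactly one earlier surveillance colonoscopy, whereas at month 48 the standard arm has had two and the relaxed arm one. Month 48 is therefore a comparison of whole strategies and not simply the same endpoint corrected. That stands. It is also the comparison that the objective describes, and it is why the protocol must say how earlier recurrences count.

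A reader might go further and infer that the trial is unsound because it has no non-inferiority margin, or that its size is wrong (it "will enroll approximately 760 patients undergoing pEMR"). The documents do not support this. The protocol gives no margin and no basis for 760, but a statistical analysis plan that is not shown may give both. Nor is 760 shown to be wrong. With the usual formula at one-sided 2.5%, n per arm = (z_0.975 + z_power)² × 2p(1-p)/margin², quite different assumed designs reach it:

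- rate 2%, margin 3 points, 80% power: 342 per arm, and 684/0.90 = 760 with 10% loss;
- rate 4%, margin 5 points, 90% power: 323 per arm, and 646/0.85 = 760 with 15% loss.

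A reader might also take the hypothesis's wording as a zero-tolerance test, or take "The study showed no significant difference in recurrence rates between the standard group" as the standard for success. The first sits beside an explicit non-inferiority objective. The second reports the retrospective study and is not a decision rule for this trial.

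**Conclusion.** The primary endpoint as written compares month 18 with month 48, with 12 versus 36 months since the previous colonoscopy. This conflicts with the hypothesis and with the stated purpose of the 48-month standard-arm visit. The timetable fits neither arm's SC2 and is one year short for the relaxed arm under any reading of the endpoint.

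The conclusion rests only on the protocol's schedules and on SC2 meaning what the protocol says it means. No recurrence rate is assumed. For the same reason, no figure is given here for the bias or for lost power: it would depend on recurrence rates at 18 and 48 months that the documents do not supply. The absence of a margin and of a basis for 760 is noted only, and is not part of the finding.

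**What to change.** Before any outcome data are seen:

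1. Reconcile the abstract, Groups and Follow-Up, and Primary Endpoint so that the primary endpoint is compared at the same time from the index procedure in both arms. The 48-month colonoscopy already scheduled in both arms serves. Name the month and not only the visit number, and do the same for the secondary endpoint set at SC2.
2. State whether recurrences found and treated at earlier visits count towards the primary endpoint. The arms have different numbers of earlier examinations (two and one), so the answer affects what is compared.
3. Correct the timetable to 5-6 years, or explain from what point the 36 months are counted.

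No visit is added and no schedule changes. The cost is that the standard arm's primary result comes 48 - 18 = 30 months later, with more loss to follow-up to be expected by then. The relaxed arm already has to wait until month 48, so the end of the trial does not move.

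### Does counting the standard arm's 48-month colonoscopy as part of the standard strategy build a false saving into the cost-effectiveness comparison?

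*Protocol*

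**What the plan says.** The abstract's Objectives and Hypotheses sets "a relaxed surveillance strategy involving fewer colonoscopies (12 and 48 months") against "the standard intensive strategy (6, 18, and 48 months"). The abstract's Methods repeats the two schedules: "Colonoscopies at 6, 18, and 48 months after the index procedure" for the standard group and "Colonoscopies at 12 and 48 months after the index procedure" for the relaxed group.

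Groups and Follow-Up in the main text describes the standard arm in two steps. First: "Patients will undergo surveillance colonoscopy at 6 and 18 months after the index procedure". Then: "The standard surveillance group will have an additional colonoscopy at 48 months in order to converge the timeline with the delayed group". The relaxed arm's exams at 12 and 48 months are given together in a single sentence.

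Secondary Endpoints includes "comparative cost effectiveness of both surveillance strategies" and says nothing further about costing.

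**The concern.** The two descriptions seem to give the same exam a different status. In the abstract, month 48 is one of the three exams that define the comparator. In Groups and Follow-Up it is an extra, and the only reason given is to bring the two timelines together. Background and Aim points the same way: its account of the currently recommended schedule stops at a second exam one year after the first and mentions no exam at 48 months.

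The protocol presents fewer procedures and lower costs as the benefit of relaxed surveillance. If the third standard exam is there only for the trial, an analyst who follows the abstract would charge a research procedure to usual care and credit the relaxed arm with avoiding it. The saving in the cost-effectiveness endpoint could then be too large. Only that secondary endpoint is at stake here. Which exam counts as SC2 in the standard arm for the primary endpoint is a separate question.

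**Working it through.** **Inputs.** Standard schedule 6, 18 and 48 months; relaxed schedule 12 and 48 months (abstract, and Groups and Follow-Up). About 760 patients (abstract, Methods), allocated 1:1 (Study Design), so 760 / 2 = 380 per arm. Full attendance is assumed.

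**The protocol's own count.** Per patient through month 48: 3 standard exams against 2 relaxed, so one fewer. This agrees with the stated objective. In total: 380 × 3 = 1140 against 380 × 2 = 760; the difference is 380, and 380 / 1140 = 33.3%.

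**Month 48 removed from the standard arm only.** 380 × 2 = 760 against 760; difference 0.

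**Cumulative exams per patient:**

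| Through month | Standard | Standard without month 48 | Relaxed |
|---|---|---|---|
| 6 | 1 | 1 | 0 |
| 12 | 1 | 1 | 1 |
| 18 | 2 | 2 | 1 |
| 47 | 2 | 2 | 1 |
| 48 | 3 | 2 | 2 |

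From month 18 to month 47 the relaxed arm is one exam behind, whatever the third standard exam is called. The zero appears only at month 48, because the relaxed arm's exam at that month is counted and the standard arm's is not. That sets standard follow-up ending at month 18 against relaxed follow-up ending at month 48.

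**Month 48 treated alike in both arms:**

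- Counted in both: 3 − 2 = 1 per patient; 1140 − 760 = 380 exams (33.3%).
- Left out of both: 2 − 1 = 1 per patient; 760 − 380 = 380 exams (380 / 760 = 50%).

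The absolute saving is the same. On this reading, one exam at 12 months replaces two at 6 and 18 months, and month 48 is common to both arms.

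**Usual care.** Let f be the share of standard patients who would have an exam between months 18 and 48 outside the trial, with the relaxed arm keeping its 48-month exam. The saving is 380 × f:

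- f = 0: 0 exams
- f = 0.1: 38 exams
- f = 0.5: 190 of 760 + 190 = 950 (20.0%)
- f = 1: 380 of 1140 (33.3%)

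The protocol does not give f, and relabelling the exam would not supply it.

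**The case for a change.** The strongest case for acting is that the wording does differ, and in a telling way: the relaxed arm's 48-month exam is ordinary surveillance, while the standard arm's is an addition with a design reason. An author of the economic analysis could follow either description, and the count through month 48 would then show a saving of one third or none. One sentence of clarification and one extra analysis would cost little.

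The difference in wording stands, and so does the caution that a trial-driven exam should not be charged to usual care without thought. The rest is weaker:

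- **The descriptions are compatible.** Every section gives the same three standard visits. Groups and Follow-Up explains why the third falls where it does; it does not call it a study-only procedure or exclude it from the strategy.
- **No rule is stated wrongly.** The protocol names the endpoint and stops. Perspective, horizon, cost items and the treatment of trial-driven exams are commonly settled in a statistical or economic plan, and one may exist that is not shown.
- **The extra analysis would not settle the matter.** Dropping the exam from one arm gives unequal follow-up for both costs and findings. The real usual-care saving depends on f, which neither version estimates.

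**Conclusion.** No change to the plan follows. The tension lies in how one exam is described, not in what is done to patients or in any stated analysis. The counts of 3 versus 2 and 2 versus 2 are both arithmetically right, but the second depends on removing month 48 from one arm only. With that month handled alike in both arms, the relaxed schedule has one exam fewer per patient, or 380 in all, assuming 380 per arm and full attendance.

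If the exam is purely trial-driven, the usual-care saving could be anywhere from 0 to 380 exams, depending on a share that the protocol does not report. Whoever writes the economic analysis will in any case have to say how trial-driven exams are costed and use the same horizon in both arms. That is a gap analysts fill as a matter of course, and it touches one secondary endpoint only.

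### The primary endpoint is read at the second surveillance colonoscopy, which falls at month 18 in the standard arm and month 48 in the relaxed arm, so timing is confounded with arm

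*Protocol*

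**What the plan says.** - **Primary Endpoint section:** "The primary endpoint is the rate of residual or recurrent adenoma at the second surveillance colonoscopy (SC2), comparing the relaxed and standard surveillance groups". The visit is identified by its order, with no month.
- **Groups and Follow-Up, standard arm:** "Patients will undergo surveillance colonoscopy at 6 and 18 months after the index procedure", followed by: "The standard surveillance group will have an additional colonoscopy at 48 months in order to converge the timeline with the delayed group".
- **Groups and Follow-Up, relaxed arm:** "Patients will undergo surveillance colonoscopy at 12 and 48 months after the index procedure".
- **Abstract, Objectives and Hypotheses:** the aim is to show that the relaxed strategy "is non-inferior to the standard intensive strategy (6, 18, and 48 months) in management of residual or recurrent disease". The hypothesis is that it "does not increase the rate of residual or recurrent adenoma detected at long-term follow-up".
- **Background and Aim:** current practice is described "with SC1 performed 3-6 months after the initial procedure and SC2 one year after SC1".
- **Timetable:** "1-2 years for recruitment and an additional 36 months for follow-up to SC2", giving 4-5 years in all.
- **Secondary Endpoints:** new or missed polyps are also counted at SC2.

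**The concern.** Naming the endpoint by visit number works only if that visit falls at the same time in both arms. Here it does not. Time since the index procedure and time since the previous examination both differ by arm, so a difference in recurrence at SC2 mixes the effect of the strategy with the effect of looking at different times.

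The direction of the distortion is not known in advance. Recurrence that becomes visible in months 18-48 can count only against the relaxed arm. Recurrence that becomes visible in months 6-12 can count only against the standard arm, because the relaxed arm finds it at its first examination. Depending on when recurrences appear, the trial could fail to show a non-inferiority that is true or declare one that is false. The second is the more serious error, because the Protocol expects the result to bear on surveillance guidelines.

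**Working it through.** **Step 1. Count the examinations (Groups and Follow-Up).**

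| | Standard | Relaxed | Gap |
|---|---|---|---|
| First surveillance (SC1) | month 6 | month 12 | 6 months |
| Second surveillance (SC2) | month 18 | month 48 | 48 - 18 = 30 months |
| Third | month 48 | none | |
| SC1 to SC2 | 18 - 6 = 12 months | 48 - 12 = 36 months | 24 months |

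The Timetable's 36 months to SC2 matches neither month 18 nor month 48 from index. It equals only the relaxed arm's interval from SC1 to SC2. Recruitment of 12-24 months plus 36 gives 48-60 months, which is the stated 4-5 years. Recruitment plus 48 gives 60-72 months, or 5-6 years.

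**Step 2. Illustration with constant risk.** Assume the same yearly risk q after SC1 in both arms, with each examination clearing what it finds.

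- As written: standard = q (12 months); relaxed = 1 - (1 - q)^3 (36 months).
- Both read at month 48: standard = 1 - (1 - q)^2.5 (30 months since month 18); relaxed unchanged.

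| Assumed q per year | Standard, month 18 | Relaxed, month 48 | Difference as written | Difference, both at month 48 |
|---|---|---|---|---|
| 0% | 0 | 0 | 0 | 0 |
| 1% | 1.00% | 2.97% | +1.97 | +0.49 |
| 2% | 2.00% | 5.88% | +3.88 | +0.96 |
| 3% | 3.00% | 8.73% | +5.73 | +1.40 |
| 4% | 4.00% | 11.53% | +7.53 | +1.82 |

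Differences are relaxed minus standard, in percentage points. For scale, Background and Aim puts recurrence at SC1 after margin ablation at 3-5%.

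**Step 3. Illustration with front-loaded recurrence.** Let E(a-b) be the share of patients whose recurrence becomes visible between months a and b. Assume it is the same in both arms, that E(6-48) totals 4%, and that it falls by a ratio r = 2^(-6/half-life) every six months.

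- As written: standard = E(6-12) + E(12-18); relaxed = E(12-18) + E(18-48). Difference = E(18-48) - E(6-12).
- Both at month 48: standard = E(18-48); relaxed = E(12-18) + E(18-48). Difference = E(12-18).

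| Assumed pattern | E(18-48) - E(6-12), as written | E(12-18), both at month 48 |
|---|---|---|
| Even over time | 2.86 - 0.57 = +2.29 | +0.57 |
| Rate halves every 12 months | 1.81 - 1.29 = +0.52 | +0.91 |
| Rate halves every 6 months | 0.98 - 2.02 = -1.04 | +1.01 |
| Rate halves every 3 months | 0.25 - 3.00 = -2.75 | +0.75 |

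The as-written difference is zero when r^2 + r^3 + r^4 + r^5 + r^6 = 1. That gives r = 0.637, a half-life of about 9.2 months. With both arms read at month 48, the difference has the same sign in every case.

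**The case against.** The best reply is that this is a labelling slip and not a design flaw. The month-48 standard examination exists only to align the arms, both strategies in the objective end at month 48, the hypothesis concerns long-term follow-up, and the Timetable gives a single time to SC2. The authors probably mean a common final examination. That is plausible, but nothing ties the endpoint to month 48. The text says second, and it calls the month-48 standard examination additional. An analyst who follows it would use month 18. If month 48 is meant, the wording still has to change. Nor is this a detail for the statistical analysis plan, because the Protocol itself fixes the visit.

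Several narrower objections have some force:

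- **The Background sentence on SC2 describes current practice, not the trial arms.** It is supporting evidence only. The visit count stands without it.
- **The sizes are all assumptions.** They run from -2.8 to +7.5 points and include zero. The largest requires an 11.5% rate in the relaxed arm, well above the 3-5% quoted for SC1. False non-inferiority needs strongly early recurrence, for which the Protocol gives no evidence either way. The figures show that the bias can be material and of either sign. They do not estimate it.
- **Clearance is not perfect.** Background and Aim gives 2-4% residual disease at SC2 after treatment at SC1. Read as applying to treated recurrences, this is at most 5% x 4% = 0.2% of all patients, too little to change the picture.
- **Reading at month 48 does not always shrink the difference.** In Step 3, +0.5 becomes +0.9 and -1.0 becomes +1.0. What remains is the effect of the standard arm's extra month-18 examination, which belongs to the strategies being compared. It does not come from reading the arms at different times from index.
- **The timetable slip is a separate planning error.** It needs correcting but does not itself show bias.

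**Conclusion.** The point holds: the primary endpoint is wrong as written and must be corrected. The visit it names is 30 months later from index in the relaxed arm, with three times the interval since the previous examination, and it leaves out the standard-arm visit that would make the arms comparable. This follows from the Protocol's own schedule and needs no assumption.

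The size does rest on assumptions: equal biology in both arms, examinations that clear what is visible, and assumed rates. Under constant risk of 1-4% per year the timing-only difference is 2.0 to 7.5 points against the relaxed arm. With 4% total recurrence over months 6-48 it ranges from +2.3 to -2.8 points, changing sign at a half-life of about 9 months. If risk after SC1 is close to zero, the distortion is small, but the Protocol gives no basis for assuming that.

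**What to change.** 1. Define the primary endpoint as residual or recurrent adenoma at the resection site at the month-48 colonoscopy in both arms (third examination in the standard arm, second in the relaxed arm). Use the month in place of the SC2 label.
2. State how recurrences found and treated before month 48 count in that endpoint, since the arms have different numbers of earlier examinations.
3. Report the SC1 rates and the standard arm's month-18 rate as descriptive secondary results.
4. Read new or missed polyps at the month-48 examination in both arms.
5. Correct the Timetable to 48 months of follow-up, which is 5-6 years with the stated recruitment.

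The cost is low. Both arms already have the month-48 examination, and the analysis must wait for the relaxed arm's in any case. There are two downsides: more standard-arm drop-out by month 48 than by month 18, and a need to check the basis for 760 patients, which the Protocol does not show, against the expected month-48 rate. The change should be made before month-18 results exist, so that it cannot appear to be driven by the data.
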